SURGICAL PROCEDURE INFORMATION

1. Surgeon Name:

2. Description of Surgical procedure:

 1 Coronary Artery Bypass Graft (CABG)	 7 Liver Resection
 2 Re-do CABG	 8 Total Splenectomy
 3 Aortic Valve Repair	 9 On-clamp Partial Nephrectomy
 4 Re-do Aortic Valve Repair	 10 Radical Nephrectomy
 5 Mitral Valve Repair	 11 Other, please specify, including type of implant or graft, if applicable: 
 6 Re-do Mitral Valve Repair	

3. Was aspirin use discontinued prior to surgery? 1 Yes 0 No N/A
if yes, how far in advance of surgery was aspirin use discontinued?

4. Please describe any concomitant procedures, if applicable:

BLEEDING SITE INFORMATION

5. Bleeding site to be evaluated (please select one):

 1 Cardiac procedure: epicardium	 6 Cardiac procedure: aortic anastomosis or aortotomy suture line
 2 Liver resection: resected liver surface	
 3 Total splenectomy: retroperitoneal surface	
 4 On-clamp partial nephrectomy: kidney bed	
 5 Radical nephrectomy: retroperitoneal cavity	

6. Conventional means for hemostasis performed before assessment of bleeding (select all that apply):

 1 Suture
 2 Clips
 3 Electrocautery
 4 Argon beam coagulator
 5 Reversal of coagulopathy
 6 Staples
 7 Other, please specify all: 

Subject Initials: Subject Number: Visit Type: ³ Intraoperative

BLEEDING SEVERITY ASSESSMENT					
7. Mass (g) of packaged, sterile gauze:					
8. Mass (g) of 2 packaged 5g bellows – PERCLOT:					
9. Mass (g) of 2 packaged 5g bellows – ARISTA:					

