7 MINUTE ASSESSMENT OF HEMOSTASIS

48. Has hemostasis been achieved?

 ₁ Yes ₀ No

49. Time of Assessment

HH:MM:SS (24-hour clock)

 : :

50. Was the study device dislodged during gauze removal?

 ₁ Yes ₀ No

51. Was dislodgement perceived to be the sole reason for hemostatic failure?

 ₁ Yes ₂ No ₀ N/A

If hemostasis is confirmed at 7 minutes, observe site for an additional 5 minutes.

ADDITIONAL 5 MINUTE OBSERVATION FOR MAINTENANCE OF HEMOSTASIS

52. Was hemostasis maintained for the additional 5 minute observation period (12 minutes post-application)?

 ₁ Yes ₂ No ₀ N/A

53. Time of Assessment:

HH:MM:SS (24-hour clock)

 : :
 ₀ N/A

If breakthrough bleeding occurs during additional 5 minute observation, document that time as the Time of Assessment.

ADDITIONAL HEMOSTATIC MEASURES

54. If hemostasis was not achieved at 7 minutes, or if hemostasis was achieved at 7 minutes but not maintained through the additional 5 minute observation (12 minutes post-application), what alternative means of achieving hemostasis were used (check all that apply):

 a. Stitches
If checked, specify # of stitches:
 b. Manual pressure applied
If checked, specify time (minutes):
 c. Other hemostatic device
If checked, specify:
 d. Other
If checked, specify:
 e. No additional actions were taken or products used

 Not applicable

Form completed by: _____

Date form completed: ___ / ___ / ___

Subject Initials: Subject Number: Visit Type: ³ Intraoperative

POST HEMOSTASIS ASSESSMENTS (Prior to Closure)

55. Volume of fluid used to rinse away excess Study Device: mL

56. After saline irrigation and aspiration, estimate the amount of hemostatic material remaining in this subject in relation to the original amount applied and document the amount of saline irrigation used:

- 1 Approximately 0% - almost all or all of the material was removed
- 2 Approximately 25% - about 75% of the material was removed
- 3 Approximately 50% - about 50% of the material was removed
- 4 Approximately 75% - about 25% of the material was removed
- 5 Approximately 100% - very little or none of the material was removed

57. Blood pressure:

a. Diastolic: mmHg

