22	
a. If hemostasis was achieved at 7 minutes observe site until 12 minutes to assess maintenance of hemostasis. After the 12 minute observation period, remove excess RSD carefully by gentle saline irrigation and aspiration. Cardiac patients who have received PerClot only: Following the application of PerClot for epicardial bleeding within the pericardial cavity and achievement of hemostasis, the pericardial cavity should be rinsed with up to 70cc of fluid per 1 gram of PerClot in order to ensure removal of excess particles.
 
b. If hemostasis was not achieved at 7 minutes or if hemostasis was not maintained at any point during the additional 5 minute observation period or beyond (12 minute post-application), the surgeon may employ alternative means of achieving hemostasis.
	
a. If applicable, record actual time at additional 5 minute assessment (12 minutes post-application). If breakthrough occurs, record actual time of breakthrough.
 
b. Record any alternative means for achieving hemostasis.
 
c. Record the volume of fluid used to rinse away excess RSD and the estimated amount of study device remaining following irrigation.

23	a. Estimate the amount of RSD left in the patient in relation to the original amount applied (percentage) after careful and complete saline irrigation and aspiration of excess material, if applicable.	
24		
a. Return not assigned RSD to investigational drug pharmacy or accountability center and any remaining assigned RSD/packaging. Used RSD packaging is to be kept throughout patient study duration.

25	
a. Prior to surgical closure, verify hemostasis maintenance. If hemostasis is not maintained, the surgeon may employ alternative means of achieving hemostasis.
	
a. Record verification of hemostasis maintenance.
 
b. Record any alternative means for achieving hemostasis, if applicable.

RESUME all Post-Operative Safety and Data Instructions.

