4.2.3 Trial Success Criteria

Trial success will be the rejection of the primary efficacy null hypothesis, with the upper bound of the 97.5% one-sided confidence interval for the difference in proportions of subjects achieving hemostasis at 7 minutes between treatment groups ($P_{Control} - P_{PerClot}$) being less than 0.10, in the As Treated population.

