4.6 Covariate Analysis

Covariate analyses will be performed to assess the association with certain study parameters on the primary efficacy endpoint. These models will be fit using logistic regression, measuring the odds of primary efficacy success. All models will include treatment group as a covariate. Covariates found to be significant at a 0.1 alpha level in the univariate assessment will be included in a multivariable model. After the multivariable model is fit, covariates will remain in the final multivariable model if they maintain significance at a 0.1 alpha level. For both univariate and multivariate models, the model derived estimates (i.e. beta estimates) for the association with primary efficacy success will be displayed, along with the Type III p-values. An adjusted estimate of the difference between proportions and associated 95% confidence interval (treatment versus control) will be obtained from the multivariable model.

Covariate assessments may consist of, but are not limited to, the following variables:

- Demographic measures such as age, gender, ethnicity, and BMI;
- Medical history;
- Therapeutic area;

- Use of blood modifiers or products known to affect bleeding (including aspirin and colloids);;
- Administration of blood products;
- Fluids administered (including colloids and crystalloids);
- Surface area of the anatomic site;
- Initial bleeding severity (as continuous measure);
- Indication for surgery;
- Complete blood count and coagulation status;
- Complement C3;
- Smoking history;
- Use of oral contraceptives;
- Diabetes;
- Presence of any malignancies;
- Amount of hemostat applied;
- Core body temperature;
- Level of glycosylated hemoglobin;
- Other hemostatic efforts made;
- Procedure type;
- NNIS risk index;
- Blood glucose at randomization;
- Blood glucose within 1 hour of device application;
- American Society of Anesthesiologists Classification;
- Total operative time;
- Placement of wound drain;
- Drainage volume within 24 hours postoperatively;
- Total drainage volume;
- Total drainage duration; and
- Volume of fluid used to rinse away excess study device.

In the event that a covariate is significant at the 0.05 alpha level in the univariate assessment, an additional model will be fit to test for an interaction effect of treatment and that covariate.

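### SAP 4.6 takes an adjusted treatment difference from a model whose candidate covariates include variables measured after, and possibly caused by, the 7-minute outcome

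*SAP*

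**What the plan says.** SAP 4.6 fits logistic models for 7-minute hemostasis with treatment in every model. Entry is by significance alone: "Covariates found to be significant at a 0.1 alpha level in the univariate assessment will be included in a multivariable model". A covariate then stays if it still meets the 0.1 level. From the resulting model: "An adjusted estimate of the difference between proportions and associated 95% confidence interval (treatment versus control) will be obtained from the multivariable model".

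The list is permissive and open-ended. It mixes baseline variables with later ones, for example "Drainage volume within 24 hours postoperatively". It also includes items without a time point, for example "Other hemostatic efforts made". Neither the SAP nor Protocol 6.6.11, which carries essentially the same list, restricts candidates by when they are measured. Protocol 6.6.11 does not promise an adjusted difference; only SAP 4.6 does.

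The adjusted estimate does not decide the trial. SAP 4.2.3 says: "Trial success will be the rejection of the primary efficacy null hypothesis", and that test uses the unadjusted difference in the As Treated population.

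**The concern.** A covariate-adjusted difference estimates the treatment effect if the covariates are fixed before treatment. If a covariate is a consequence of the outcome, conditioning on it absorbs part of the effect. If it depends on both arm and outcome, conditioning can create a difference where none exists.

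The screening rule gives no protection. A variable driven by the outcome is strongly associated with it, so it tends to be selected.

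At stake is a treatment difference with a 95% interval that readers will set beside the primary result, and that may wrongly appear to confirm or contradict it.

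**Working it through.** **Timing of the candidates, from the documents**

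- *After the 7-minute assessment:* total operative time (to skin closure, Protocol 6.4.3.5), drain placement (Operative form Q61, prior to closure), 24-hour and total drainage volume, drainage duration and rinse volume. The NNIS index also depends on operation duration.
- *Rinse volume* can depend on both outcome and arm. Appendix N step 22 says, for subjects hemostatic at 7 minutes: "After the 12 minute observation period, remove excess RSD carefully by gentle saline irrigation and aspiration". The same step adds a pericardial rinse after epicardial use for PerClot subjects only.
- *At or after application, so open to a device effect:* amount of hemostat applied and glucose within 1 hour.
- *Undated:* other hemostatic efforts, blood products, fluids, blood modifiers, core temperature, blood count and coagulation, and C3. Temperature is recorded before and after application. Blood count, coagulation and C3 are drawn before and after surgery.
- *Other hemostatic efforts* has several possible sources. Operative form Q6 precedes eligibility: "Conventional means for hemostasis performed before assessment of bleeding". Q54 applies only "If hemostasis was not achieved at 7 minutes, or if hemostasis was achieved at 7 minutes but not maintained" through 12 minutes, so it nearly restates the outcome. Q63 and Q69 are further late sources.

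Total operative time and units transfused are also safety endpoints in SAP 4.4.4, as are alternative means of hemostasis.

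**The plan's own figure.** SAP 4.6 states no number. The design calculation in SAP Appendix A (Farrington-Manning score test, 90% against 90%, margin 0.10, one-sided 0.025, 154 per arm) reproduces at power 0.79885. The simulations use 154 per arm.

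**Exact check, rescue-type yes/no variable.** Differences are PerClot minus control. Assume true success of 80% and 90%, and a variable C recorded in 70% of failures and 5% of successes in both arms.

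- P(C=1): PerClot 0.2×0.7 + 0.8×0.05 = 0.18; control 0.1×0.7 + 0.9×0.05 = 0.115; pooled 0.1475.
- Success given C=1: 0.04/0.18 = 0.222 and 0.045/0.115 = 0.391; difference -0.169.
- Success given C=0: 0.76/0.82 = 0.927 and 0.855/0.885 = 0.966; difference -0.039.
- Standardised difference: 0.1475×(-0.169) + 0.8525×(-0.039) = -0.058, or -5.8 points instead of -10.

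The odds ratio is 4/9 in both strata, so the logistic model fits exactly; the shrinkage comes from conditioning on C. With 50% and 90% use in failures the same steps give -7.6 and -3.8. Simulation (2,000 trials each) gave -7.7, -5.9 and -4.0 for 50%, 70% and 90%.

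**Continuous covariate driven only by the outcome.** C is N(0,1) plus a shift in failures. The model has treatment and C, with C kept if p<0.1. The risk difference is standardised with a delta-method interval (4,000 trials per cell; Monte Carlo SE 0.05 to 0.08 points).

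| Shift (SD) | C kept | Mean adjusted difference, true -10 | Mean lower limit |
|---|---|---|---|
| 0.25 | 46% | -9.9 | -17.7 |
| 0.5 | 92% | -9.8 | -17.5 |
| 0.75 | 99.8% | -9.3 | -16.8 |
| 1.0 | 100% | -8.7 | -16.1 |
| 1.5 | 100% | -7.3 | -13.9 |

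The unadjusted lower limit is about -17.9. Numerical integration of the same model gives large-sample values of -9.9, -9.7, -9.3, -8.7 and -7.2. For true 85% against 90% the simulated means are -4.8, -4.5 and -3.6 at 0.5, 1.0 and 1.5 SD. For 90% against 90% they are 0.0 at every shift.

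**Covariate affected by arm as well.** Suppose C is raised by 0.5 to 2.0 SD in failures and also shifted by 0.5 SD across the PerClot arm.

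- True -10, arm shift upward: -6.8, -3.4, -0.4 and +1.3 points at 0.5, 1.0, 1.5 and 2.0 SD.
- True -10, arm shift downward: between -12.6 and -14.2.
- Equal rates: about +2.1 to +5.4 with the upward shift, and -2.3 to -5.4 with the downward shift.

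A milder case mimics rinse volume: C is raised by success, and by the device in one third of PerClot subjects. At equal rates it gives -0.1, -0.6 and -1.5 points at 0.25, 0.5 and 0.8 SD.

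**Both selection steps.** With eight noise covariates added and both entry and retention applied, a true -10 became -10.1, -8.6 and -7.1 at 0.5, 1.0 and 1.5 SD. It became -7.7 and -4.0 for the rescue-type variable at 50% and 90% use. The outcome-driven covariate was kept in 91% to 100% of runs.

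**Pre-application covariate only.** With one prognostic covariate fixed before application (log-odds 0.5 to 1.5 per SD) and a true -10.0, the mean adjusted difference was -10.0 to -10.2.

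**The case against.** The strongest reply is that this is an exploratory association analysis. SAP 4.6 gives its purpose as assessing associations, the list is permissive, no text compares the adjusted difference with the 0.10 margin, and the SAP applies the term supportive to the ITT and Per Protocol analyses, not to this one. Association models containing later variables are not an error. All of that stands. It does not remove the commitment to report an adjusted treatment difference with an interval from the selected model, and a permissive list leaves the choice of variables to be made after the data are seen.

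A second reply concerns size. The shifts have no documentary basis. Under the design assumption of equal rates, a covariate driven only by the outcome causes no bias in the point estimate. At a true -10, shifts up to 0.5 SD hardly matter, and 1.0 SD moves the estimate by 1.3 points against an interval half-width near 8. This stands: material distortion needs a stronger link to the outcome, an arm effect, or the rescue-measure reading.

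That reading is itself arguable, because the SAP elsewhere calls post-failure measures alternative means. But Q54 sits under a form heading about additional hemostatic measures, so the ambiguity is real. The one-third share in the rinse case is probably high, since the PerClot-only step concerns epicardial bleeding and cardiac eligibility also covers aortic suture lines. The NNIS route is weak: contaminated and dirty wounds are excluded, so only ASA class and the duration threshold vary.

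**Conclusion.** The concern holds. Following SAP 4.6 as written can produce an adjusted treatment difference that does not estimate the treatment effect.

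With an outcome-driven covariate and a true difference, the estimate shrinks toward zero: negligibly up to 0.5 SD, from -10 to about -7.3 points at 1.5 SD, and to between -7.7 and -4.0 if a rescue-type variable enters. If the device also affects the covariate, the error can go either way and can arise even when true rates are equal. These sizes rest on assumed associations.

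The primary conclusion, type I error, power and sample size are not touched.

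**What to change.** In SAP 4.6, add one or two sentences limiting candidates for the adjusted-difference model to variables fixed before device application:

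- therapeutic area, procedure and indication;
- initial bleeding severity and anatomic site area;
- demographics, medical history and ASA class;
- preoperative laboratory values, including C3 and HbA1c;
- preoperative blood modifiers and aspirin;
- glucose at randomization and pre-application core temperature;
- hemostatic efforts from Operative form Q6 only.

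Report post-application variables, NNIS and any item without a defined pre-application time point as descriptive associations, with no treatment-effect estimate taken from those models. Protocol 6.6.11 needs at most a conforming note. No new data are required, and the analysis becomes slightly smaller.

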6.6.11 Covariate Analysis Methods

Covariate analyses will be performed to assess the association with certain study parameters on the primary efficacy endpoint. For these analyses, logistic regression models will be used. Covariates will be tested univariately for inclusion in the multivariate model. Covariate assessments may consist of, but are not limited to, the following variables:

- Demographic measures such as age, gender, ethnicity, and BMI;
- Medical history;
- Therapeutic area;
- Use of blood modifiers or products known to affect bleeding (including aspirin and colloids);
- Administrations of blood products;
- Fluids administered (including colloids and crystalloids);
- Surface area of the anatomic site;
- Initial bleeding severity (as continuous measure);
- Indication for surgery;
- Complete blood count and coagulation status;
- Complement C3;
- Smoking history;
- Use of oral contraceptives;
- Diabetes;
- Presence of any malignancies;
- Amount of hemostat applied;
- Core body temperature;
- Level of glycosylated hemoglobin;
- Other hemostatic efforts made;
- Procedure type;
- NNIS risk index;
- Blood glucose at randomization;
- Blood glucose within 1 hour of device application;

- American Society of Anesthesiologists Classification;
- Total operative time;
- Placement of wound drain;
- Drainage volume within 24 hours postoperatively;
- Total drainage volume;
- Total drainage duration; and
- Volume of fluid used to rinse away excess study device.

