4.4.4 Safety Analyses

Safety data will be summarized by incidence of each adverse event type along with 95% exact confidence intervals. Adverse event rates will be reported as the proportion of subjects who experience an event and the total number of each event type occurring.

Adverse events will be summarized by relatedness, seriousness, and severity. The comparison of safety between treatment arms will be based on Fisher's exact tests for the proportion of subjects with serious device-related adverse events, unanticipated adverse device effects, and frequent adverse events ($\geq 5\%$ overall incidence) in the two treatment groups.

The other following safety endpoints will also be summarized using descriptive statistics:

- Total operative time;
- Hemostasis at 5 to 7 minutes;
- Hemostasis maintenance;
- Total intraoperative estimated blood loss;
- Alternative means required to achieve hemostasis (where applicable);
- Units of blood transfused intraoperatively and postoperatively (where applicable);
- Incidence of reoperation;
- Total hospitalization time;
- Incidence of procedure complications;
- Incidence of adverse events through final follow-up, including, but not limited to:
 - Adhesions or fibrosis;
 - Anaphylaxis;
 - Blockage of the bladder or ureteral lumen;
 - Blockage of the bypass system;
 - Cancer recurrence and/or progression;
 - Compromised attachment of prosthetic devices to bone or tissue;
 - Death;
 - Embolism;
 - Failure of deep or superficial wound healing;
 - Failure to obtain hemostasis;
 - Fever;
 - Hemorrhage;
 - Infection;
 - Peri-operative hyperglycemia;
 - Exacerbation of surgical procedure-associated adverse events;
 - Swelling and compression of pressure-sensitive tissues and structures;
 - Thromboembolism;
 - Thrombosis; and
 - Toxicity.

Safety analyses are descriptive in nature. There are no formal hypothesis tests associated with these outcomes. All safety analyses will be performed on the ITT population.

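### The adjusted treatment difference in SAP 4.6 can be adjusted for variables measured after the 7-minute outcome

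*SAP*

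**What the plan says.** SAP 4.6 fits logistic models for 7-minute hemostasis, all with treatment group included. The entry rule is "Covariates found to be significant at a 0.1 alpha level in the univariate assessment will be included in a multivariable model". A covariate stays if it keeps that significance level, and from the resulting model "An adjusted estimate of the difference between proportions and associated 95% confidence interval (treatment versus control) will be obtained from the multivariable model". Protocol 6.6.11 carries the same list and the rule "Covariates will be tested univariately for inclusion in the multivariate model". Neither section limits candidates to baseline or pre-outcome variables, and both lists are open-ended.

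These listed candidates come late:

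- "Drainage volume within 24 hours postoperatively": a postoperative assessment (Protocol 6.4.4).
- Total drainage volume and duration: discharge data (Protocol 6.4.5).
- "Total operative time": runs to skin closure (Protocol 6.4.3.5) and is itself a safety endpoint in SAP 4.4.4.
- "Volume of fluid used to rinse away excess study device": recorded in the post-hemostasis block of the sample operative form (Appendix E). In the branch of Appendix N step 22a for hemostasis achieved at 7 minutes, the instruction is "After the 12 minute observation period, remove excess RSD carefully by gentle saline irrigation and aspiration".
- Drain placement: recorded in the same block of the form, so probably also after the outcome.

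Trial success (SAP 4.2.3) rests on the confidence interval for the difference in proportions in the As Treated population, not on this model.

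**The concern.** A variable that takes its value after the outcome cannot have caused it, but may be a consequence of it. After a failure at 7 minutes the surgeon may turn to other means of hemostasis, which can lengthen the operation and change drainage. If the device also affects the variable by another route, conditioning on it distorts the comparison of arms.

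The direction depends on signs nobody knows at the planning stage. If PerClot raises drain output and failures drain more, the adjustment flatters PerClot. If PerClot subjects are rinsed more and failures less, it works against PerClot. At stake is a prespecified adjusted difference with a 95% interval, which readers would take as confirming or questioning the primary result.

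**Working it through.** **The plan's own figure.** The plan gives no figure for this model. The nearest is the power of 0.79885 with 154 per arm (SAP Appendix A). The Farrington-Manning score test, with restricted null proportions 0.831 and 0.931, reproduces it. Restricting the covariate list does not change it.

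**Assumptions (not in the documents).** One continuous covariate M in SD units; 162 per arm; Y = 1 for hemostasis at 7 minutes; A = 1 for PerClot.

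M = b(1 − Y) + cA + N(0,1)

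Here b is the shift in failures and c the shift due to the arm. SAP 4.6 does not say how a difference in proportions is obtained from a logistic model, so standardization over the sample is assumed.

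**Why bias arises.** By Bayes' rule,

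logit P(Y=1 | A, M) = logit(p_A) + b²/2 − bM + bcA

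The treatment coefficient is therefore the true log odds ratio plus b × c. Example: true success 85% PerClot and 90% control, b = 0.5, c = 0.3. The true log odds ratio is 1.735 − 2.197 = −0.463 (from unrounded logits). Adding 0.5 × 0.3 = 0.15 gives −0.313. With M always in the model, the standardized Control − PerClot difference is 3.28 points instead of 5.00. For b = 0, 0.1 and 0.3 it is 5.00, 4.67 and 3.98.

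**With the 0.1 screen.** Simulation, 4,000 trials per setting, 85% vs 90%, c = 0.3. If M has Wald p < 0.1 the standardized difference is reported; otherwise the unadjusted one.

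| b | M enters | Mean reported | Unadjusted, same trials | Move (points) |
|---|---|---|---|---|
| 0 | 9.6% | 5.08 | 5.08 | 0.0 |
| 0.1 | 16.1% | 4.93 | 5.10 | −0.2 |
| 0.3 | 54.7% | 4.26 | 5.04 | −0.8 |
| 0.5 | 90.4% | 3.38 | 5.04 | −1.7 |
| −0.1 | 15.4% | 5.14 | 4.99 | +0.2 |
| −0.3 | 55.1% | 5.70 | 4.98 | +0.7 |
| −0.5 | 90.2% | 6.45 | 5.04 | +1.4 |

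Positive b is the drainage pattern (failures higher); negative b is the rinse pattern (failures lower).

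**Other settings.**

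- 90% in both arms, c = 0.3: moves of −0.6 and −1.2 at b = 0.3 and 0.5, and +0.6 and +1.3 at b = −0.3 and −0.5.
- No arm shift (c = 0), 85% vs 90%: 5.01 against 5.07 at b = 0.3, and 4.93 against 5.06 at b = 0.5, so about 0.1 point.
- Drainage known for half the subjects (assumed, at random, complete cases), c = 0.3: entry falls to 34% and 65% at b = 0.3 and 0.5, and the moves to −0.6 and −1.4.

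**The case against.** The strongest reply is that nothing is decided on this estimate. SAP 4.6 aims to explore associations, its list is permissive, and entry of any variable is possible rather than certain. That stands, and it limits the point to a supportive estimate. It does not remove it, because the section goes beyond associations and prespecifies an adjusted treatment difference with an interval.

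A second reply concerns the two links. The documents establish neither for drainage, which is collected only where applicable; the full-sample entry rates above are therefore upper-end for the drainage variables. This also stands.

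A reader might infer that rinse volume is tied to outcome and arm by the protocol itself. Step 22a does write removal into the success branch, and under "Cardiac patients who have received PerClot only" it adds a pericardial rinse. That does not establish the tie:

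- Step 22c and the sample form record rinse volume without limiting it to successes.
- The instructions for use (Appendix A) call for removal once hemostasis is achieved, which can also follow alternative means.
- Saline is prepared before the device-specific steps, and excess device is removed in both arms.
- The extra rinse concerns epicardial bleeding, while aortic suture-line sites are also eligible.

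Rinse volume is a plausible case, no more.

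Finally, the timing of drain placement rests on the layout of a sample form that the protocol says may differ, and much of total operative time may precede application. Hence *probably* for the former and *completed after* for the latter.

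**Conclusion.** The point holds for the adjusted estimate. As written, SAP 4.6 and Protocol 6.6.11 allow variables measured or completed after the outcome into the model that yields the adjusted treatment difference. If both links exist, that difference is biased in an unpredictable direction. Under the assumptions shown, the mean move is 0 to about 1.7 points. Within that range it is negligible if either link is absent.

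Two stronger readings are not supported. One is that the trial could wrongly succeed: the success rule uses the As Treated difference in proportions, so its type I error and the sample size are untouched. The other is that the bias runs to several points. Assumed failure shifts of 0.5 to 1.5 SD with arm shifts of 0.5 SD either way, at 154 per arm, gave moves of about 2 to 5 points with no true difference and up to about 9 points with a true difference at the margin. Nothing in the documents indicates shifts of that size.

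**What to change.** In SAP 4.6 and Protocol 6.6.11, state that the adjusted treatment difference comes only from a model restricted to variables measured before device application. Then:

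- Remove the three drainage variables, drain placement, total operative time and rinse volume from that model.
- By the same rule, leave out the NNIS index, which uses operation duration (Appendix M), and keep ASA class. Leave out whole-operation fluid and blood-product totals and glucose within 1 hour of application.
- Leave out the amount of hemostat applied. It precedes the outcome but follows assignment, so adjusting for it can remove part of the device effect.
- Use pre-application values of blood count, coagulation, C3 and core temperature, which are also measured later.
- Define other hemostatic efforts as conventional means used before the bleeding assessment, since the item could otherwise cover rescue after failure.

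Associations of the removed variables with the outcome may still be shown as exploratory. The cost is wording in two documents. No new data are needed, and the primary analysis and sample size do not change.
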